**Table 2-6: Schedule of activities- Part 2 Treatment Sequence A**

	Screening	Baseline	OC+PSL					Washout (14 Days)	OC			EOS/ SFU/ EDV a
			1	2 to 8	9	10	11		26	27	28	
Day	-29 to -2	-1	1	2 to 8	9	10	11	12 to 25	26	27	28	33 to 40
Written informed consent	X											
Demographics and baseline characteristics	X											
Inclusion /Exclusion criteria verification	X	X	X									
General medical /medications/ procedures history	X	X						X (D25)				
Suicidality Risk Assessment (C-SSRS) b	X	X						X(D25)				X
Psychiatric and mental status evaluation	X	X	X h	X h	X h	X h	X h					X
Physical examination c	X	X	X	X				X (D25)				X
Vital signs d	X	X	X	X					X	X	X	X
Pregnancy test	X	X						X (D25)				
Hematology, clinical chemistry, urinalysis	X						X	X (D25)				X
Serology (HIV, HBsAg, HEV, syphilis, and HCV-Ab)	X											
12-lead ECG	X	X	X	X e	X	X	X					X

This document cannot be used to support any marketing authorization application and any extensions or variations thereof.

REDACTED COPY for support any marketing authorization application and any extensions or variations thereof.

**Table 2-6: Schedule of activities- Part 2 Treatment Sequence A**

Day	Screening	Baseline	OC+PSL				Washout (14 Days)	OC			EOS/SFU/ EDV a	
			1	2 to 8	9	10		11	26	27		28
-29 to -2	X	X										
Urine and cotinine drug screen, and alcohol breath test												
Recording of adverse events/medical procedures	X	X	X				X (D25)					
Blood sampling for genotyping of drug metabolizing enzymes and/or transporters												
Admit to clinic		X					X (D25)					
Administer PSL			X									
Administer OC				X					X			
Blood sampling for PSL PK levels				X f					X f	X f		
Blood sampling for OC PK levels					X g						X g	X g
Blood sampling for cross-validation l					X							
Discharge							X (D12 or D13) j					X

C-SRRS=Columbia Suicide Severity Rating Scale; ECG=electrocardiogram; EDV=Early Discontinuation Visit; EOS=End of Study; h=hour(s); HbsAg-Ab=HepB surface antigen antibodies; HCV-Ab=HepC virus antibodies; HEV=hepatitis E virus; HIV=human immunodeficiency virus; OC=oral contraceptive; PK=pharmacokinetic; PSL=padsevonil; SFU=Safety Follow-Up

a If a study participant discontinues early, SFU procedures should be completed as the EDV. Upon early termination/withdrawal, the study participant will be encouraged to complete SFU assessments following the last dose of study medication.

b All study participants will complete the “Screening/Baseline” version of the C-SRRS during Screening (assessing the past 6 months), followed by the “Since Last Visit” version at subsequent visits.

c At Screening, Baseline (Day -1), and Day 8, a full physical examination will be performed. On all other days a physical examination is performed, it will be a brief physical examination (Section 8.3.1). On days 2-7, physical examination will not be performed.

d Oral or aural body temperature must be performed using the same method in any individual study participant on all occasions, pulse rate, respiratory rate, and blood pressure will be assessed. Vital signs (to be taken before blood collection for laboratory tests) will consist of 1 pulse and 1 blood pressure measurement.

e ECG will be completed on Days 2, and 8 only of multiple day periods during Treatment Sequence A.

f During the OC+PSL Treatment Period, trough levels of PSL will be collected on morning before PSL dosing on Day 2, Day 4, and Day 6. Additional blood sampling for PK analysis will be taken on Day 8 before (predose) and after PSL morning dose at 0.25h, 0.5h, 1h, 1.5h, 2h, 3h, 4h, 6h, 8h, 12h postdose and on Day 9 before (predose) and after the PSL and OC morning dose at 0.25h, 0.5h, 1h, 1.5h, 2h, 3h, 4h, 6h, 8h, 12h, 24h (before morning PSL dose on Day 10), and 48h (before morning PSL dose on Day 11) postdose.

g During OC+PSL Treatment Period, blood sampling for OC PK analysis will be taken on Day 9 (before OC+PSL morning dose) and after PSL and OC morning dose at 0.25h, 0.5h, 1h, 1.5h, 2h, 3h, 4h, 6h, 8h, 12h. In addition, blood samples will be obtained prior to the morning dose on Day 10, 36h (Day 10), and 48h (Day 11) postdose. During the single-dose OC period, PK blood samples will be taken on Day 26 at predose and 0.25h, 0.5h, 1h, 1.5h, 2h, 3h, 4h, 6h, 8h, 12h, 24h (Day 27), 36h (Day 27), and 48h (Day 28) postdose.

h Psychiatric and mental status evaluation will be done pre-dose.

i The study participant can be discharged on Day 12 or Day 13, at the discretion of the principal investigator.

j Mitra™ (finger prick) and venous blood samples will be taken at 0.5h, 1h, 3h, 6h, 12h postdose on Day 8 only for selected study participants. See Section **Error!**  
**Reference source not found.** for details about selection.

**Table 2-7: Schedule of activities- Part 2 Treatment Sequence B**

	Screening -29 to -2	Baseline -1	OC			Washout (14 Days) 4 to 17	PSL+OC				EOS/SFU EDV a 35 to 42	
			1	2	3		18	19 to 25	26	27		28
Day												
Written informed consent	X											
Demographics and baseline characteristics	X											
Inclusion /Exclusion criteria verification	X	X				X						
General medical /medications/ procedures history	X	X				X (D17)						
Suicidality Risk Assessment (C-SSRS) b	X	X				X (D17)						X
Psychiatric and mental status evaluation	X	X					X f	X f	X f	X f	X f	X
Physical examination c	X	X					X	X			X	X
Vital signs d	X	X	X				X	X	X	X	X	X
Pregnancy test	X	X				X (D17)						
Hematology, clinical chemistry, urinalysis	X	X				X(D17)					X	X
Serology (HIV, HbsAg, HEV, syphilis, and HCV-Ab)	X											
12-lead ECG	X	X	X				X	X e	X	X	X	X
Urine and cotinine drug screen, and alcohol breath test	X	X				X(D17)						

This document cannot be used to support any marketing authorization application and any extensions or variations thereof.

**Table 2-7: Schedule of activities- Part 2 Treatment Sequence B**

Day	Screening -29 to -2	Baseline -1	OC			Washout (14 Days) 4 to 17	PSL+OC			EOS/SFU EDV a 35 to 42
			1	2	3		18	19 to 25	26	
Recording of adverse events/medical procedures	X	X	X	X	X (D17)	X		X	X	X
Blood sampling for genotyping of drug metabolizing enzymes and/or transporters		X								
Admit to clinic		X			X (D17)					
Administer PSL						X		X	X	
Administer OC			X				X			
Blood sampling for PSL PK levels							X g	X g	X g	X g
Blood sampling for OC PK levels			X h	X h	X h			X h	X h	X h
Blood sampling for cross-validation j							X			
Discharge				X						X (D29 or D30) i

C-SRRS=Columbia Suicide Severity Rating Scale; ECG=electrocardiogram; EDV=Early Discontinuation Visit; EOS=End of Study; h=hour(s); HbsAg-Ab=HepB surface antigen antibodies; HCV-Ab=HepC virus antibodies; HEV=hepatitis E virus; HIV=human immunodeficiency virus; OC=oral contraceptive; PK=pharmacokinetic; PSL=padsevonil; SFU=Safety Follow-Up

a If a study participant discontinues early, SFU procedures should be completed as the EDV. Upon early termination/withdrawal, the study participant will be encouraged to complete SFU assessments following the last dose of study medication.  
b All study participants will complete the “Screening/Baseline” version of the C-SRRS during Screening (assessing the past 6 months) followed by the “Since Last Visit” version at subsequent visits.  
c At Screening, Baseline (Day -1) and Day 25, a full physical examination will be performed. On all other days a physical examination is performed, it will be a brief physical examination (Section 8.3.1). On Days 19-24, physical examination will not be performed.

d Oral or aural body temperature must be performed using the same method in any individual study participant on all occasions, pulse rate, respiratory rate, and blood pressure will be assessed. Vital signs (to be taken before blood collection for laboratory tests) will consist of 1 pulse and 1 blood pressure measurement.

e ECG will be completed on Days 19, and 25 only of multiple day periods during Treatment Sequence B.

f Psychiatric and mental evaluation will be done pre-dose.

g During the OC+PSL Treatment Period, trough levels of PSL will be collected on morning before PSL dosing on Day 19, Day 21, and Day 23. Additional blood sampling for PK analysis will be taken on Day 25 before (predose) and after PSL morning dose at 0.25h, 0.5h, 1h, 1.5h, 2h, 3h, 4h, 6h, 8h, 12h postdose and on Day 26 before (predose) and after the PSL and OC morning dose at 0.25h, 0.5h, 1h, 1.5h, 2h, 3h, 4h, 6h, 8h, 12h, 24h (Day 27), and 48h (Day 28) postdose.

h During the single-dose OC period, PK blood samples will be taken on Day 1 at predose and 0.25h, 0.5h, 1h, 1.5h, 2h, 3h, 4h, 6h, 8h, 12h, 24h (Day 2), 36h (Day 2), and 48h (Day 3) postdose. During OC+PSL Treatment Period, blood sampling for OC PK analysis will be taken on Day 26 (before OC+PSL morning dose) and after PSL and OC morning dose at 0.25h, 0.5h, 1h, 1.5h, 2h, 3h, 4h, 6h, 8h, 12h, 24h (Day 27), 36h (Day 27), and 48h (Day 28) postdose.

i The study participant can be discharged on Day 29 or Day 30, at the discretion of the principal investigator.

j Mitra™ (finger prick) and venous blood samples will be taken at 0.5h, 1h, 3h, 6h, 12h postdose on Day 25 only for selected study participants. See Section **Error!**

**Reference source not found.** for details about selection.

## 2.3 Determination of sample size

Lack of PK interaction in this study will be concluded if 90% confidence intervals for both AUC and  $C_{\max}$  geometric means ratios (with/without PSL) of LN and EE are included in the 80% to 125% bioequivalence range.

In a previous OC interaction study conducted by UCB with brivaracetam (N01282), an intra-subject coefficient of variation of 10% for  $AUC_{\tau}$  for both EE and LN (including  $C_{\max}$ ) and 16% for  $C_{\max}$  was observed for EE.

Provided that the ratio of the expected means for test (with PSL) and reference (without PSL) is included in the range [0.90, 1.10] and for a type-I error of 0.05 and an intra-subject coefficient of variation of 16%, a total sample size of 34 study participants should allow at least 90% power for the assessment of lack of interaction (or 26 study participants for 80% power).

A total of 40 study participants will be randomized: Part 1 (PSL 400mg BID) will include 14 study participants and will allow a good estimate of the different ratios of PK parameters. Part 2 (PSL 200mg BID) will include 26 study participants (13 study participants in each sequence). Assuming no drop-outs, a decrease of 10% in PK parameters of OC and intrasubject coefficient of variation of 16%, this will allow 80% power for assessing lack of PK interaction.

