## 1 INTRODUCTION

The purpose of this statistical analysis plan (SAP) is to provide all information that is necessary to perform the required statistical analysis of UP0035. It also defines the summary tables, figures and listings (TFLs) to be included in the final clinical study report (CSR) according to the protocol.

This SAP is based on the following documents:

- Original Clinical Study Protocol dated 01 Aug 2019
- Clinical Study Protocol Amendment 1 dated 10 Oct 2019
- File Note with number Ward v3 (HMR code 19-009) dated 12 Dec 2019
- Clinical Study Protocol Amendment 2 dated 25 Feb 2020

Unless specified in the sections below, the study will be analyzed as described in the most recent version of the protocol. If a future protocol amendment necessitates a substantial change to the statistical analysis of the study data, this SAP will be amended accordingly. In addition, if analysis definitions must be modified or updated prior to database lock, a SAP amendment will be required. If, after database lock, additional analyses are required to supplement the planned analyses described in this SAP, these changes will be described in the CSR together with the associated rationale.

Following UCB's decision to terminate the padsevonil (PSL) epilepsy project in partial onset seizures, the UP0035 study has been stopped and no study participants will enter study Part 2. Consequently, study results reporting will be restricted to study Part 1 of this SAP and a subset of the tables, figures, and listings will be reported in line with Clinical Trial Reporting duties (EUDRA-CT, ClinicalTrials.gov).

The content of this SAP is compatible with the International Council for Harmonisation (ICH)/Food and Drug Administration (FDA) E9 Guidance documents (Phillips et al, 2003).

UCB is the Sponsor and ICON PLC is the Contract Research Organization for this study.

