Forty (40) evaluable study participants will be enrolled overall. A total of 14 evaluable study participants (7 study participants in each sequence) have completed Part 1 with PSL 400mg BID dosing. For Part 2 with PSL 200mg BID dosing, a total of 26 evaluable study participants are planned (13 study participants in each sequence). Study participants who are withdrawn may be replaced following discussion between the Investigator and Sponsor.

In Part 1, the maximum total duration of the study is approximately 75 days for each study participant, including the Screening Period (up to 28 days), a 36-day Treatment Period including a Washout Period of at least 14 days, and a SFU Visit (the SFU Visit should occur no sooner than 7 days, and at a maximum of 10 days following the final dose of study medication). Study participants in Part 1 (either sequence) will be treated with PSL (maximum dose of 400mg BID) for a total of 19 days.

In Part 2, the maximum total duration of the study is approximately 70 days for each study participant, including the Screening Period (up to 28 days), a 28-day Treatment Period, including a 14-day Washout Period, and a SFU Visit (the SFU Visit should occur no sooner than 7 days, and at a maximum of 14 days following the final dose of study medication). Study participants in Part 2 (either sequence) will be treated with PSL (maximum dose of 200mg BID) for 11 days, a reduction of 8 days compared with Part 1.

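### SAP 2.2 and 2.3 still give 40 participants and 80% power from a cancelled Part 2; no power or precision is stated for the 14 Part 1 completers to whom the 80-125% rule now applies

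*SAP*

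**What the plan says.** SAP 1 states that "the UP0035 study has been stopped and no study participants will enter study Part 2", that "study results reporting will be restricted to study Part 1 of this SAP", and that "a subset of the tables, figures, and listings will be reported in line with Clinical Trial Reporting duties". It does not say whether the SAP 9.1 comparison belongs to that subset.

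SAP 2.2 still reads "Forty (40) evaluable study participants will be enrolled overall", of which 26 are for Part 2. It also records "A total of 14 evaluable study participants", 7 per sequence, as having completed Part 1. SAP 2.3 still reads "A total of 40 study participants will be randomized". Its only power figures are at least 90% for 34 participants and 80% for 26, and for Part 2 it concludes: "Assuming no drop-outs, a decrease of 10% in PK parameters of OC and intrasubject coefficient of variation of 16%, this will allow 80% power". Of Part 1 it says only that it "will allow a good estimate of the different ratios of PK parameters".

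SAP 2.3 sets the conclusion rule for the study as a whole: the 90% CIs for AUC and Cmax of both EE and LN must lie within 80% to 125%. SAP 9.1 repeats the rule without naming a part. It adds a second step, individual ratios above 0.7, for when the interval is slightly too wide. SAP 3.1 has PK analysed and reported separately for each part.

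**The concern.** The SAP gives two accounts of the trial. In SAP 1 only Part 1 exists. In SAP 2.2 and 2.3 there are still 40 participants, and the only quantified power belongs to cohorts that will not exist. Because PK is analysed by part, the 80-125% rule has nothing left to act on except Part 1, where the SAP offers a qualitative remark and no number.

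A reader of the final SAP could take 80% as the power behind the reported result. That matters most if Part 1 fails 80-125%: with 80% power a failure would look informative, while with 14 participants it is much less so.

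**Working it through.** **Inputs.** All are from SAP 2.3 unless stated.
- True ratio 0.90, the lower end of the planned range 0.90 to 1.10.
- Type I error 0.05, taken as one-sided for each limit (90% CI).
- Within-subject CV 16% (EE Cmax), and 10% (EE AUC, LN AUC and, as I read the sentence, LN Cmax). The 10% for AUC was observed for AUCτ and is used here for single-dose AUC.
- Part 1 size 14, as 7 + 7 (SAP 2.2).
- Predicted EE AUC ratio at 400mg BID: 1 − 0.16 = 0.84 (protocol 2.1).

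**Formulas.** Two one-sided tests (TOST) in a 2x2 crossover on the log scale:
- σ_w = √ln(1 + CV²), SE = σ_w·√(2/N), df = N − 2, t = t(0.95, df).
- Power = the average of Φ[(ln 1.25 − t·s − ln θ)/SE] − Φ[(ln 0.80 + t·s − ln θ)/SE], set to 0 where negative, over s = SE·√(χ²_df/df).
- Expected 90% CI = ratio multiplied or divided by exp(t·SE).

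**Reproducing the SAP's figures.** At ratio 0.90 and CV 16%, N = 24 gives just under 80% (79.99%), N = 26 gives 82.9% and N = 34 gives 91.1%. So 26 and 34 are the smallest balanced sizes for 80% and 90%.

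**Part 1, N = 14.**
- CV 16%: σ_w = √ln(1.0256) = 0.1590; SE = 0.1590 × √(2/14) = 0.0601; t(12) = 1.782; exp(1.782 × 0.0601) = 1.113. Power is 58.0%.
- CV 10%: σ_w = √ln(1.01) = 0.0998; SE = 0.0377; exp(1.782 × 0.0377) = 1.070. Power is 90.3%.
- With CV 16%, an observed ratio of 0.90 gives 0.90/1.113 to 0.90 × 1.113, that is 0.809 to 1.002. The rule is met when the observed ratio lies between about 0.80 × 1.113 = 0.890 and 1.25/1.113 = 1.123.
- At the other end of the planned range (ratio 1.10), power is 64.0% (CV 16%) and 93.9% (CV 10%).

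Simulation with 400,000 runs at ratio 0.90 and CV 16% gives 0.580, 0.830 and 0.911 for N = 14, 26 and 34.

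**If the PK Set is not 14.** SAP 3.5.3 defines the set by measurable concentrations and absence of important PK deviations, not by completion. At ratio 0.90:

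| N | Power, CV 16% | Power, CV 10% | CI factor, CV 16% | CI factor, CV 10% |
|---|---|---|---|---|
| 12 | 51.7% | 85.2% | 1.125 | 1.077 |
| 14 | 58.0% | 90.3% | 1.113 | 1.070 |
| 16 | 63.6% | 93.7% | 1.104 | 1.064 |
| 26 | 82.9% | 99.4% | 1.078 | 1.048 |

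**All four parameters together.** The joint probability cannot exceed that of the weakest parameter, 58.0%. Under independence, which is an assumption, it would be 0.580 × 0.903³ = about 43%. The documents give no correlations.

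**At the predicted EE AUC ratio of 0.84, CV 10%.** Power is 33.6% at N = 14, 52.7% at N = 26 and 69.3% at N = 40.

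These figures cover the 80-125% step only. The chance of a favourable declaration under SAP 9.1 is higher to the extent that the >0.7 step is used, and the wording of that step does not allow a calculation.

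**The case against.** Section 2 of the SAP is headed as a protocol summary, and SAP 2.3 repeats protocol 9.9. SAP 1 comes first and overrides it openly. The 80% is tied to Part 2 only, the Part 1 size of 14 is stated and was reached, and Part 1 is given an estimation aim. The observed 90% CI will show the precision achieved. All of this stands and limits the weight of the point. It does not remove the mismatch, because SAP 9.1 is an operative analysis section and its rule is not limited by part.

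Three stronger readings are tempting, and the documents do not support them:
- **The sample size is wrong.** It reproduces.
- **A Part 1 pass is not valid, or the SAP 9.1 rule should become descriptive.** With a 90% CI, TOST holds the risk of a false pass at 5% per parameter at any N. Low power makes a pass less likely, not less valid. Dropping the rule would also depart from protocol 9.3 after open-label Part 1 dosing, when staff analysing PK could see data during the study (protocol 6.3).
- **The cancellation caused the low power at a ratio of 0.84.** Even 26 participants would give only about 53% there.

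**Conclusion.** The point holds as a failure to update the SAP. The size and power in SAP 2.2 and 2.3 describe a trial that SAP 1 says will not happen, and the cohort now subject to the 80-125% rule has no stated power or precision. On the SAP's inputs, power falls from the stated 80% (82.9% exact at 26) to about 58% for the CV 16% parameter, so the full four-parameter rule would fail at least 42% of the time (100 − 58) at a true ratio of 0.90. For the CV 10% parameters power is about 90%, but that figure does not apply to EE AUC at the protocol's own prediction for 400mg BID, where it is about 34%.

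This rests on balanced sequences with both periods observed, the CVs of the earlier interaction study, a PK Set near 14, and the SAP 9.1 comparison being among the outputs reported. No estimate or interval changes.

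**What to change.** In SAP 2.2 and 2.3, mark the 40-participant, 26-participant and 80% power statements as the plan before termination, superseded by SAP 1. Then add to SAP 2.3 text such as:

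> Part 1 has 14 completers; the PK Set may differ. At a true ratio of 0.90 and CV 16%, power to meet 80-125% is about 58% (52% with 12 participants, 64% with 16), and the expected 90% CI is the ratio multiplied or divided by about 1.11. At CV 10%, power is about 90% and the factor about 1.07. Power for all four parameters together is at most 58%. At the predicted EE AUC ratio of 0.84 for 400mg BID and CV 10%, power is about 34%, and would be about 53% with 26 participants. These figures cover the 80-125% step only, not the >0.7 step.

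Keep the SAP 9.1 decision rule. At most, add that failing 80-125% in Part 1 is not by itself evidence of an interaction, because power is low.

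The cost is a few sentences in the SAP. No participants, data or analyses are added, and the prespecified rule is unchanged.

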## 3 DATA ANALYSIS CONSIDERATIONS

### 3.1 General presentation of summaries and analyses

Statistical evaluation will be performed by ICON PLC and supervised by UCB. The datasets will follow the UCB analysis data model (ADaM) data specifications. All statistical analyses will be performed using SAS® Version 9.4 or later (SAS Institute, Cary, NC, USA).

Pharmacokinetic parameters will be determined by non-compartmental analysis (NCA) with Pharsight Phoenix® WinNonlin® Build 8.0 or higher (Certara L.P., Princeton, NJ, NCA) software. Pharmacokinetic analyses will be performed and reported for each study part. PK parameter estimation will use actual doses administered and the actual sampling times relative to time of dose administration.

Categorical endpoints will be summarized using number of study participants (n), frequency, and percentages. Missing data will not be imputed. Individual plasma concentrations and PK parameters will be presented using 3 significant digits.

When reporting relative frequencies or other percentage values, the following rules apply:

- For values where all study participants fulfill certain criteria, the percentage value will be displayed as 100
- For values where the absolute frequency is zero, there will be no percentage displayed
- All other percentage displays will use 1 decimal place

Percentages displayed based on continuous data (e.g. percentage changes from baseline) will be displayed to 1 decimal place. Unless otherwise stated, the denominator for the percentages will be based on the number of study participants in the respective analysis set.

Continuous variables will be summarized by day and time point (where applicable) including number of study participants (n), mean, median, standard deviation (sd), minimum and maximum. Geometric coefficient of variation (geoCV), geometric mean and 95% confidence interval (CI) for the geometric mean will also be presented in the descriptive statistics for the plasma concentrations and PK parameters for EE, LN, PSL and its metabolites ( [REDACTED] [REDACTED] ] and [REDACTED] ). In all outputs, the confidence limits will be restricted to the possible values that the variable can take.

Venous plasma samples will be obtained for EE, LN, PSL and its metabolites.

When reporting descriptive statistics, the following rules will apply in general except for PK concentration data (plasma and blood (PK) of EE, LN, PSL and its metabolites ( [REDACTED] [REDACTED] and [REDACTED] )):

- n will be an integer
- Mean (arithmetic and geometric), standard deviation and median will use 1 decimal place more, or 1 significant figure more – depending on the reporting format of the original data – than the original data
- Confidence intervals will use 1 decimal place more, or 1 significant figure more – depending on the reporting format of the original data – than the value around which the confidence interval is constructed
- Coefficient of variation (CV) will be reported as a percentage to 1 decimal place
- Minimum and maximum will be reported using the same number of decimal places or significant figures as the original value
- If no study participants have data at a given time point, then only n=0 will be presented. If n<3, then only the n, minimum and maximum will be presented. If n=3, then only n, minimum, median and maximum will be presented. The other descriptive statistics will be left blank.

When reporting individual values and descriptive statistics for PK concentration data (EE, NL, PSL and its metabolites ( [REDACTED] and [REDACTED] [REDACTED] )), the following rules will apply regarding rounding and precision:

- Individual values for PK concentration data will be reported to the same level of precision as received from the bioanalytical laboratory
- Descriptive statistics for PK concentration data will be reported to the same level of precision as the individual data for the minimum and maximum, and to 1 additional decimal place or 1 additional significant figure– depending on the reporting format of the original data with a maximum of 3 significant digits - for the mean (arithmetic and geometric), median and standard deviation. The 95% CI for the geometric mean will use 1 decimal place more, or 1

significant figure more – depending on the reporting format of the original data – than the value around which the confidence interval is constructed

- Geometric CV will be reported as a percentage to 1 decimal place

When reporting individual values and descriptive statistics for PK parameters (PK of EE, LN, PSL and its metabolites ( [REDACTED] and [REDACTED] )) the following rules will apply with regard to rounding and precision:

- Individual values for PK parameters will be reported to 3 significant figures
- Descriptive statistics for PK parameters should be rounded to 4 significant figures for the mean, median and standard deviation and to 3 for the others

Data listings containing all documented data and all derived data will be generated and presented by treatment sequence (treatment sequence A and treatment sequence B) and treatment period.

